5-7	Experimental Sessions 1-3. Subjects complete 1 sample and 5 choice trials to receive cocaine (0, 10 and 30 mg/70 kg) or money (\$6.00) by responding on the concurrent progressive-ratio schedule. Assessment battery completed following administration of the sampling dose as described below.
8-9	Washout. Placebo administered twice daily (0700 and 1900 hours).
10-15	Zolmitriptan (2.5 mg/day) maintenance. Administered in divided doses (0700 and 1900 hours).
13-15	Experimental Sessions 4-6. Details are the same as for days 5-7.
16-17	Washout. Placebo administered twice daily (0700 and 1900 hours).
18-23	Zolmitriptan (5 mg/day) maintenance. Administered in divided doses (0700 and 1900 hours).
21-23	Experimental Sessions 7-9. Details are the same as for days 5-7.
24-25	Washout. Placebo administered twice daily (0700 and 1900 hours).
26-31	Zolmitriptan (10 mg/day) maintenance. Administered in divided doses (0700 and 1900 hours).
29-31	Experimental Sessions 10-12. Details are the same as for days 5-7.
32	Discharge.
Note	Dosing order is illustrative. All doses will be administered in random order.

This experiment will require each subject to participate for approximately one month. Experimental sessions will be conducted as outlined in Table 1 above. We would like to note four important points relating to the table above: 1) To avoid experimental testing on weekends, subjects may be maintained on zolmitriptan or placebo for longer than outlined above (i.e., maintenance conditions may last for two days longer than in the example above). 2) The order of zolmitriptan maintenance conditions and cocaine experimental sessions will be randomized. 3) All maintenance conditions will be followed by a two-day washout period in which the participant receives a placebo delivered in a double-blinded fashion. 4) If subjects leave the protocol for a reason unrelated to study procedures (e.g., a family emergency or dental problems), they may be re-admitted

with physician approval to complete the remainder of the protocol, picking up in the condition where they left off (i.e., sessions/dose conditions that have already been completed will not be repeated). Thus, they may not complete the protocol over one approximately 33-day admission but can complete the protocol over two admissions totaling approximately 33 days.

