Cardiovascular Measures and Body Temperature. Heart rate, blood pressure, cardiac rhythmicity (i.e., electrocardiograms [ECG]) and body temperature will be recorded before cocaine administration and at frequent intervals after dose administration. Cardiac rhythmicity (i.e., electrocardiograms [ECG]) will be recorded for 30 minutes before intravenous cocaine administration and continuously during each experimental session. No drugs will be administered if a subject's heart rate is \geq 90 bpm if systolic pressure \geq 140 or diastolic pressure \geq 90 mmHg. A subject will be excluded from further participation if at any time he or she exceeds our cardiovascular safety and tolerability thresholds (i.e., heart rate above 130 bpm, diastolic pressure increases above 120 mmHg or systolic pressure above 180 mmHg or clinically significant ECG changes) after administration of zolmitriptan alone, cocaine alone or cocaine-zolmitriptan combinations. Heart rhythmicity will be assessed via 3-lead telemetry continuously during each experimental session, will be printed out and verified as normal prior to dose administration, and will be monitored continuously for a minimum of 15 minutes following each infusion.

Safety and tolerability outcomes: Udvalg for Kliniske Undersøgelser (UKU). The UKU is a standardized, validated rating scale that assesses over 50 potential side effects (e.g., sedation, akathisia, weight change) associated with administration of centrally acting drugs (Lingjaerde et al., 1987). It also includes a global assessment of how these side effects interfere with functioning. This questionnaire will be completed daily at 1630 h. We have routinely used this scale to evaluate the safety and tolerability of maintenance doses and cocaine ([name] et al., 2008; [name] et al., 2009; [name] et al., 2007; 2008; 2016). A subject will be excluded from further participation if at any time he or she exceeds adverse event safety and tolerability thresholds (i.e., an effect rated as severe lasting more than 24 h) after drug administration.

Drug Dose and Administration. All drugs will be administered under double-blind conditions and medical supervision in randomized order. We currently hold an IND for intravenous cocaine administration and will modify it to test intravenous cocaine during zolmitriptan maintenance. To maintain the blind, only [name] and the Investigational Drug Service will have access to dose conditions for subjects.

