Data Analysis. All data will be analyzed statistically as outlined below using SPSS. Only data from completing subjects will be included in the analyses. Any subjects who do not complete the study will be replaced until we accrue 20 completers. Statistical significance refers to $p \leq 0.05$.

Aim 1: Demonstrate that 5-HT_{1b} activation reduces the reinforcing effects of cocaine. The reinforcing effects of cocaine will be determined by evaluation of break points for cocaine and money from the concurrent progressive-ratio choice task. For cocaine and money break points, each of which have one data point for each dose condition, data will be analyzed using two-factor repeated-measures ANOVA. Cocaine (0, 10, and 30 mg/70 kg) and zolmitriptan (0, 2.5, 5, and 10 mg/day) will be factors for these analyses. A significant augmentation (i.e., leftward shift in the dose-response curve) or attenuation (i.e., rightward shift in the dose-response curve) of the effects of cocaine will be inferred if the main effect of the zolmitriptan or the cocaine-zolmitriptan interaction attains statistical significance in the ANOVA. If the cocaine-zolmitriptan interaction attains statistical significance, the Mean Square Error (MSE) term will be used to conduct Tukey's HSD *post-hoc* test to make appropriate pair-wise comparisons between means.

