Physiological data. Three sets of analyses will be conducted on the cardiovascular outcomes and body temperature data. First, data will be analyzed as peak effect using two-factor repeated-measures ANOVA. Cocaine (0, 10, and 30 mg/70 kg) and zolmitriptan (0, 2.5, 5, and 10 mg/day) will be factors for these analyses. A significant augmentation or attenuation of the effects of cocaine will be inferred if the main effect of the zolmitriptan or the cocaine-zolmitriptan interaction attains statistical significance in the ANOVA. If the cocaine-zolmitriptan interaction attains statistical significance, the MSE term will be used to conduct Tukey's HSD *post-hoc* test to make appropriate pair-wise comparisons between means. Second, AUC will be calculated for each subject using the trapezoidal method and analyzed in the same fashion as peak-effect data. Third, these data will be analyzed by repeated-measure ANOVA with cocaine, zolmitriptan and time as factors. The MSE term for the cocaine-zolmitriptan-time interaction will then be used to make appropriate pair-wise comparisons.

Safety and tolerability data. For items from the UKU, which will have one data point per day, data will be analyzed using a two-factor repeated-measures ANOVA. Zolmitriptan (0, 2.5, 5, and 10 mg/day) and day will be factors for these analyses. The MSE term for the zolmitriptan-day interaction will then be used to make appropriate pair-wise comparisons.

Evaluating Relevant Biological Variables. We will conduct exploratory analyses to evaluate potential effects of relevant biological variables. Specifically, we will repeat the analyses described above including factors like sex, age, race, and other drug use to determine whether and how these variables might influence study outcomes. Although exploratory, these outcomes can inform future grant applications in terms of how individual differences influence responses to 5-HT_{1b} activation in people with cocaine use disorder.

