As described above, Drs. [name], [name], and [name] will screen all potential subjects for physical and psychiatric contraindications to participation. Urine samples will be monitored throughout each study to ensure that female subjects are not pregnant and that all subjects are adhering to the drug use restrictions. All subjects in these studies will be thoroughly informed of the various drug side-effects which they might experience and will be appropriately cautioned concerning their activities in the hours after drug administration. However, this should not pose a significant problem because research subjects will always be under the direct supervision of the nursing staff on the CRU during drug dosing. Participation is voluntary, so individuals can withdraw at any time if they find the behavioral procedures or drug effects undesirable. The drug doses to be administered in the present experiments were chosen to minimize, if not eliminate, the chance of these side effects occurring. As noted above, Drs. [name], [name], and [name] will screen all potential research subjects for medical contraindications, and [name] of the University of Kentucky Gill Heart & Vascular Institute will review the ECG, prior to study participation. Drs. [name], [name], and [name] will monitor research subjects throughout their participation. We anticipate that careful subject selection, dose selection and subject monitoring will greatly reduce, if not eliminate, the occurrence of serious side effects. The assembled team of investigators has been conducting inpatient and outpatient human behavioral pharmacology studies with healthy subjects and subjects with histories of drug abuse for more than 60 years combined and have never observed a serious drug-related unanticipated serious adverse event. To monitor for adverse events/side effects, the UKU Side Effects Rating Scale will be completed daily with subjects by CRU nursing staff. Staff observations, subjective-effects drug effects and spontaneous subject report will also be used to monitor for adverse events.

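### Cardiovascular and UKU comparisons by zolmitriptan dose leave out subjects stopped for a reaction, so they can understate a zolmitriptan-related increase

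*Combined protocol and SAP*

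**What the plan says.** Section 7, Data Analysis, opens with the analysis set: "Only data from completing subjects will be included in the analyses". The next sentence adds "Any subjects who do not complete the study will be replaced until we accrue 20 completers". Section 4 plans 30 enrolled subjects for 20 completers.

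The safety paragraphs later in that section name no other set. For physiology: "Three sets of analyses will be conducted on the cardiovascular outcomes and body temperature data". For side effects: "For items from the UKU, which will have one data point per day, data will be analyzed using a two-factor repeated-measures ANOVA". Section 17 ranks both as tertiary.

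Subjects can leave because of a reaction in three ways:
- Section 7, Cardiovascular Measures: "A subject will be excluded from further participation if at any time he or she exceeds our cardiovascular safety and tolerability thresholds". The limits are heart rate above 130 bpm, systolic pressure above 180 mmHg, diastolic pressure above 120 mmHg, or clinically significant ECG changes. They apply to zolmitriptan, cocaine or both. Section 10 repeats them.
- Section 7, under the UKU scale, stops a subject for "an effect rated as severe lasting more than 24 h".
- Section 10: "Participation is voluntary, so individuals can withdraw at any time if they find the behavioral procedures or drug effects undesirable".

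The only re-admission route, in section 7 after Table 1, is for other causes: "If subjects leave the protocol for a reason unrelated to study procedures (e.g., a family emergency or dental problems), they may be re-admitted".

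**The concern.** The variables that remove a subject are the variables then compared by dose. A subject stopped for a reaction has no stated route back, is replaced, and normally leaves the comparison with all data, including the reading that triggered the stop. That is selection on the outcome.

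The condition that gives the selection a direction is realistic. Section 9 lists raised heart rate and blood pressure among the common side effects of zolmitriptan, and says that side effects may change when the drugs are combined. The Day 1 medical safety session gives cocaine before any zolmitriptan, so it cannot screen out subjects who react only to the combination.

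At stake is how a finding of no safety difference by dose is read. Part of such a result could come from the stopping rules.

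**Working it through.** **1. Figures in the documents.** The plan gives no expected stop rate and no blood pressure mean or SD, so it has no figure of its own to reproduce here. Enrolment allows 30 − 20 = 10 non-completers for any reason. Section 10 reports two exclusions on these criteria in 20 years of cocaine studies.

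**2. What follows without arithmetic.** A crossing means a stop, a stopped subject is not a completer, and a non-completer is not analysed. Crossings and severe effects beyond 24 h are therefore almost absent from the analysed set, whatever their true rate. The exception is one at the very end of participation, because the plan does not define a completing subject.

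**3. Illustration for mean systolic pressure; all inputs assumed.** Session peak = cocaine-dose mean + subject effect (SD 10) + fraction × subject's maximum zolmitriptan rise + session error. The fraction is 0, 0.25, 0.5 or 1 for the four zolmitriptan conditions. A Day 1 cocaine-only screen at 180 comes first, then twelve sessions in random order, with removal at the first peak above 180. The contrast is highest zolmitriptan dose minus placebo at the top cocaine dose.

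| Scenario | Cocaine means | Mean rise | Error SD |
|---|---|---|---|
| S1 | 130/135/140 | 10 | 8 |
| S2 | 130/138/145 | 10 | 8 |
| S3 | 130/140/150 | 10 | 10 |
| S4 | 130/140/150 | 15 | 10 |

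Difference in completers (mmHg), with the share stopped after Day 1:

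| SD of individual response | S1 (true 10) | S2 (true 10) | S3 (true 10) | S4 (true 15) |
|---|---|---|---|---|
| 0 | 9.90 (1.6%) | 9.78 (3.8%) | 9.26 (12.4%) | 13.58 (19.7%) |
| 4 | 9.82 (1.9%) | 9.61 (4.4%) | 8.98 (13.2%) | 13.25 (20.8%) |
| 8 | 9.49 (3.4%) | 9.11 (6.4%) | 8.15 (15.7%) | 12.06 (23.2%) |
| 12 | 8.73 (5.8%) | 8.07 (9.5%) | 6.75 (18.7%) | 10.31 (26.4%) |

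Dilution = (true − completer) / true. With identical responses it runs from (10 − 9.90)/10 = 1% to (15 − 13.58)/15 = 9%. Against the standard error at n = 20, that is 0.10/2.52 = 0.04 to 1.42/3.00 = 0.47. At SD 12, an extreme that exceeds the mean rise in three of the four scenarios, dilution reaches (10 − 6.75)/10 = 33% in S3, and the bias reaches 1.27 standard errors in S4.

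**4. No mean effect.** With a mean rise of 0 and response SD 12, stops are still more frequent at the highest dose, and the completer difference is about −0.4 to −1.3 mmHg. The bias is downward, which is not always towards zero.

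**5. Stops by condition, response SD 0.** Highest dose versus placebo: 1.10% vs 0.07% in S1, up to 13.1% vs 0.85% in S4. Per 30 dosed subjects that is 30 × 0.011 = 0.3 up to 30 × 0.131 = 3.9 at the highest dose. Completers show 0 vs 0, or at most 1.07% vs 0.04% if last-session crossers count as completers.

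**6. UKU item.** Assume a share q of subjects score 3 at the highest dose and are stopped, the rest score 0.4, and the placebo score is 0.2. The all-subject difference is 3q + 0.4(1 − q) − 0.2, which gives 0.33, 0.46 and 0.72 at q = 5%, 10% and 20%. In completers it is 0.4 − 0.2 = 0.20 each time.

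**7. Effect of the entry limit.** Section 4 excludes persistent hypertension (140/80 or above), which step 3 ignores. Capping usual systolic pressure below 140, an assumed proxy, lowers stops at response SD 0 from 1.6/3.8/12.4/19.7% to about 0.1/0.5/5.4/11.0%.

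**The case against.** The strongest case is that the effect may be negligible. Two exclusions in 20 years suggest that stops are rare. The illustration omits the entry limit, the heart rate and blood pressure limits that must be met before each dose, and section 10's definition of a crossing as sustained over five minutes. Most of these omissions inflate the stop rate, and in S1 with identical responses the bias is only 0.04 of a standard error. This stands: the size is unknown and may be small. But the history has no denominator and does not concern this combination, and even one or two stops at one dose would be tolerability information that the planned comparison discards.

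A second objection is that section 17 already has adverse events collected, reviewed weekly and followed up, and serious ones reported to the IRB, NIDA and the FDA. That is correct, and surveillance of stopped subjects is not in question. The gap is narrower: no comparison or table by zolmitriptan dose includes them.

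A third is that a mixed model cannot fully repair the selection. Stops may follow heart rate, ECG or a lasting side effect when systolic pressure is the outcome. They may also follow a choice-trial infusion, whereas the peak effect is defined only under Aim 2, and there from the sampling dose. This also stands, and it limits what the fix can promise.

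**Conclusion.** The concern holds in a limited form. As written, the tertiary cardiovascular and UKU comparisons select on their own outcome. If zolmitriptan makes stops more likely, a true increase is understated, and a zero mean effect with varied responses can look slightly negative. Crossings and lasting severe effects are nearly absent by construction. The dilution figures rest entirely on assumed inputs.

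A reader might infer more than the documents support:
- *That the comparisons always lean towards no difference.* Step 4 shows otherwise.
- *That these are the only planned tolerability comparisons by dose.* They are not. The questionnaires in Appendix A include items on bad effects, racing heartbeat, nausea and dizziness, and Aim 2 analyses the subjective data by dose under the same completer rule.
- *That the primary result is biased.* Nothing here shows that for break points. Stops on cocaine alone, including Day 1, do not by themselves bias the zolmitriptan contrast.
- *That every safety outcome is equally affected.* Body temperature has no removal limit, so any bias there is indirect. Severe effects of 24 h or less stay in.

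This should be fixed, but it does not threaten the primary aim.

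**What to change.** 1. Limit the completers-only sentence to the efficacy analyses, and state whether a subject who crosses a limit in the last session counts as completing.
2. Analyse cardiovascular and UKU data in every subject who received study drug, using all data up to and including the stop. Repeated-measures ANOVA needs every cell, so the method must accept incomplete data, for example a mixed model with a random subject term. State that this reduces the bias and may not remove it. In the illustration, a random-intercept model gave 10.00/10.01/10.00/14.99 at response SD 0 but 9.50/9.27/8.91/13.47 at SD 12.
3. Add a table of safety stops and withdrawals for drug effects by the zolmitriptan and cocaine condition in force, with the number exposed to each. List Day 1 stops separately.
4. Reconcile section 7, which gives no duration for a cardiovascular crossing, with section 10, which defines it over five minutes. The wording decides who is removed.

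The primary ANOVA and accrual to 20 completers stay as they are. The cost is some SAP wording, one table, slightly more analysis work and a missing-at-random assumption. That assumption is plausible for stops triggered by recorded readings and weaker for voluntary withdrawals. In simulated trials of 20 completers, precision was about the same (SD of the estimate 3.0 to 3.9 mmHg for mixed models, 3.0 to 3.8 for completers).

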To minimize the risk associated with intravenous cocaine administration, dosing will occur under the supervision of ACLS-certified medical staff ([name] and CRU nurses). During the medical safety and experimental sessions, heart rate and blood pressure will be recorded 30 minutes prior to cocaine administration and at frequent intervals (i.e., 15 – 30 minutes) afterwards for the duration of the session. Electrocardiograms (ECG) will be recorded continuously during each experimental session. Electrocardiograms (ECG) will be recorded continuously during the medical safety and each experimental session. Cardiovascular hypersensitivity is defined as heart rate > 130 bpm, systolic pressure > 180 mmHg or diastolic pressure > 120 mmHg elevated consistently across a five-minute period of monitoring. Cardiovascular hypersensitivity also includes prolonged abnormal heart rhythmicity, which is defined as ventricular arrhythmias that occur at a frequency greater than 5 per minute, are multifocal, or occur as couplets (2 consecutive beats) or salvos (3 or more consecutive beats) and persist for greater than 15 min. Subjects that exhibit hypersensitivity (i.e., heart rate >130 bpm, systolic pressure > 180 mmHg, diastolic pressure > 120 mmHg, or clinically significant ECG changes) to the cardiovascular effects of cocaine and/or zolmitriptan at any point during this study will be excluded immediately from further research participation and will be followed until symptom resolution. In our previous studies with cocaine over the last 20 years, only two subjects have been excluded based on these criteria. Drs. [name], [name], [name], [name], [name] and [name] will train all staff on this project. No drugs (i.e., cocaine or zolmitriptan) will be administered if a subject's heart rate is \geq 90 bpm if systolic pressure \geq 140 or diastolic pressure \geq 90 mmHg. Heart rhythmicity will be recorded continuously via 3-lead telemetry during each experimental session and will be monitored continuously for a minimum of 15 minutes following each infusion. Ischemia or other abnormalities as described in the exclusion criteria would also be cause for discharge. A cardiovascular emergency will be managed using UK medical center procedures (i.e., response from a code blue team).

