As noted above, serious side effects of stimulants include seizures. The occurrence of seizures appears to be related to the presence of certain predisposing factors including histories of head trauma, seizures or CNS tumors and the administration of concomitant medications that lower seizure threshold. Subjects that report personal histories of head trauma, seizures or CNS tumors or a first-degree family history of seizures will be excluded from research participation. Most seizures resolve of their own accord and typically, individuals with a history of seizures will be the only ones who require intervention. If a seizure should occur, we will follow the expert guidance/protocol of the UK Department of Neurology Rapid Response Team for seizure management, and [name] therapy preference, which consists of the following:

1. Assess and support respiratory and cardiac status.
2. If seizure is sustained for > 5 min, give immediate therapy with IV lorazepam (0.1 mg/kg/dose; max 4 mg/dose).
3. Repeat therapy every 5 min as need for continued/repeat seizures.

A physician in Neurology will be consulted if a second treatment dose is required. If the seizure has not stopped within the allotted time, diazepam is to be administered by the attending physician or their designee. Because we exclude individuals with a history or risk of seizures, it is very unlikely that a subject will have a seizure or that we will need to administer diazepam. If a research subject experiences a seizure, he/she will be excluded from further research participation.

Potential subjects must meet criteria for cocaine use disorder to be enrolled in the proposed experiments. It is possible that these subjects will experience abstinence symptoms once admitted to the CRU. As noted above, we have several safeguards in place to monitor for adverse events. If a subject experiences significant abstinence symptoms following admission to the CRU, he or she will be treated in accordance with the standard practice of the University of Kentucky Hospital and then dismissed from the study.

To avoid potential drug interactions, volunteers taking any prescribed medication chronically, except birth control, will be excluded. The medical personnel on this protocol will determine if it is safe for a potential volunteer to discontinue taking their medication during their participation.

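### The completers-only rule also governs the cardiovascular and side-effect analyses, so subjects stopped early for safety are missing from the planned by-dose safety results

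*Combined protocol and SAP*

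**What the plan says.** The combined protocol and SAP has one Data Analysis part, in Section 7. It opens by saying that all data will be analysed as set out there, and continues: "Only data from completing subjects will be included in the analyses". The next sentence is "Any subjects who do not complete the study will be replaced until we accrue 20 completers". The paragraphs on physiological data and on safety and tolerability data belong to the same part. Both use repeated-measures ANOVA, and neither names another population. Section 17 lists physiological and side effects as tertiary outcomes, to be analysed by zolmitriptan maintenance condition.

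Four routes lead from a poorly tolerated drug effect to non-completion:

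- **Cardiovascular or ECG limits.** Section 7: "A subject will be excluded from further participation if at any time he or she exceeds our cardiovascular safety and tolerability thresholds". Section 10 says that subjects who show hypersensitivity "at any point during this study will be excluded immediately from further research participation".
- **UKU side effects.** Section 7 stops a subject for "an effect rated as severe lasting more than 24 h".
- **Seizure.** Section 10: "If a research subject experiences a seizure, he/she will be excluded from further research participation".
- **Own choice.** Section 10: "individuals can withdraw at any time if they find the behavioral procedures or drug effects undesirable".

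Section 7 allows re-admission to finish the remaining conditions only when the reason for leaving had nothing to do with study procedures.

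**The concern.** A completer analysis is a common convenience in a small within-subject study. For safety outcomes it creates a specific problem, because the events that end participation are extreme values of the variables being analysed. A subject whose blood pressure crosses the limit at 10 mg/day of zolmitriptan with cocaine is dropped from the blood pressure analysis in every condition and replaced by someone who got through all of them. The final set of 20 then looks complete.

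Section 9 says that the side effects of the two drugs may change when they are combined, and Section 1 calls the area unstudied in humans. The by-dose safety comparison is where a reader would look for a cardiovascular or tolerability signal from the combination. As written, it describes only people who tolerated every dose.

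**Working it through.** **1. Scope of the rule.** The completer sentence is unqualified and comes before all the analysis paragraphs. The physiological and UKU paragraphs set no other population, and Section 17 repeats repeated-measures ANOVA for these outcomes without a safety set. Nothing elsewhere exempts them.

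**2. What still reaches a report.** Section 17 collects all adverse events through a 1-month follow-up, reviews them weekly and follows them to resolution. It sends every serious event to the IRB, NIDA and FDA, with an annual summary. It plans no count by zolmitriptan or cocaine condition and no denominators.

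**3. Who is lost and who is not.**
- Lost: anyone stopped before finishing, with all sessions and daily UKU ratings up to that point.
- Not necessarily lost: a severe effect lasting under 24 h. A brief excursion may also stay if Section 10's qualifier applies ("elevated consistently across a five-minute period of monitoring"); the Section 7 wording has no such qualifier.
- Unclear: an exclusion in the last session, because completion is not defined for that case.
- Separate: a subject stopped at the Day 1 medical safety session has had cocaine but no zolmitriptan, and could not inform the zolmitriptan comparison in any case.

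**4. Room for non-completion.** Section 4 plans 30 enrolled for 20 completers. That allows (30 − 20)/30 = 33% not to complete; the check is 20/(1 − 1/3) = 30. The plan does not say how many of these 10 might be safety stops.

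**5. Evidence on frequency.** Section 10 says that two subjects were excluded on the cardiovascular criteria over 20 years of the group's cocaine studies. There is no denominator, the zolmitriptan combination is not covered, and UKU stops and withdrawals are not included. It points to a low frequency but is not a rate.

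**6. What a count would show.** Assume s safety exclusions among the planned 30, with exact (Clopper-Pearson) 95% intervals:

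| Exclusions s | s/30 | Exact 95% CI | Shown in completer analyses |
|---|---|---|---|
| 1 | 3.3% | 0.1 to 17.2% | 0 of 20 |
| 2 | 6.7% | 0.8 to 22.1% | 0 of 20 |
| 4 | 13.3% | 3.8 to 30.7% | 0 of 20 |

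The values of s are illustrations. The last column holds by construction for any s, provided the stop comes before the subject finishes.

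**7. Effect on means.** As a rough guide, assume that peak systolic pressure in one condition is normal with mean μ and SD σ, and that values above 180 mmHg are removed. With a = (180 − μ)/σ, the mean falls by σφ(a)/Φ(a).
- μ = 150, σ = 12: a = 2.5, 0.6% removed, mean lower by 0.2 mmHg.
- μ = 160, σ = 15: a = 1.33, 9.1% removed, mean lower by 2.7 mmHg.

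These means and SDs are assumptions, and the five-minute qualifier and the pre-dose hold are not modelled. A removed subject leaves every condition, so part of the shift would cancel in a within-subject contrast between doses.

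**The case against.** The strongest reply is that safety oversight does not depend on the ANOVA. Adverse events of stopped subjects are recorded, followed and, if serious, reported to three bodies, and the completer rule does not forbid a descriptive table covering everyone. This stands. A reader might infer that stopped subjects disappear from all safety reporting, and the documents do not support that. What is absent is a planned summary by condition. A threshold exclusion also need not be a serious event, so SAE reporting does not fill the gap.

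Second, the only experience quoted is two cardiovascular exclusions in 20 years. This also stands as a caution. It argues against assuming several exclusions in this trial, but it cannot settle the rate for a combination not studied before.

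Third, the bias in means is likely to be small. A reader might infer that the by-dose means will be seriously distorted. That would need a minority of subjects with very large reactions, for which the documents give no basis.

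Fourth, these outcomes are tertiary, and repeated-measures ANOVA needs complete data. That can justify completers for the ANOVA. It does not justify planning no count or listing for the others.

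Finally, an exclusion on active drug would not by itself show a zolmitriptan effect. Three of the four conditions are active, so with equal risk in each condition about 3/4 = 75% of exclusions would fall there by chance. Placebo therefore belongs in the table.

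**Conclusion.** The point holds in a limited form. Followed as written, the plan gives by-dose cardiovascular and side-effect results selected on tolerability, because the rule that defines the analysed set removes subjects for the outcomes being analysed. This rests on the text alone and needs no assumed event rate.

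The size is unknown. Exclusions may be few, and the shift in mean values is probably small. The main loss is the stopping events themselves: one to four of them on 30 enrolled would be 3.3% to 13.3%, with wide intervals, and the completer analyses would show none. Those figures assume that all 30 are enrolled and that each stop comes before the subject finishes.

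The change is worth making before analysis because it is cheap and concerns the safety of a new drug combination. It does not bear on the primary break-point result.

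**What to change.** In the Data Analysis part of Section 7, exempt safety data from the completer rule and report them for all subjects given at least one maintenance dose. Add:

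1. A descriptive table by zolmitriptan condition, including placebo, and by session cocaine dose. For each cell, give subjects exposed, safety exclusions, subjects with any AE and subjects with any SAE, with exact intervals and no significance test.
2. A listing of each safety exclusion or drug-effect withdrawal, with its condition and session. List Day 1 exclusions separately as pre-zolmitriptan.

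State whether a subject excluded in the last session counts as a completer. A mixed model using all available cardiovascular and UKU data, placed beside the completer ANOVA, is optional.

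The cost is a few lines of plan, one table and one listing, from data already collected. Counts will be small and stopped subjects will not have entered later conditions, so the output is estimation only. The sample size and the primary analysis stay as they are.
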